#### **5.1.2.1 The BMS-986218 Monotherapy Escalation (Part 1A)**

Up to approximately 108 DLT-evaluable participants will be treated during the BMS-986218 Monotherapy Escalation (Part 1A) of the study for the Q4W schedule. Each participant will be

administered IV doses of BMS-986218 in planned flat dose levels of 2, 4, 7, 20, 40, 70, 100, 150, and 200 mg Q4W per cycle, for up to 2 calendar years. If supported by clinical and safety data, doses higher than 200 mg may be studied until MTD is reached, and further details will be provided in a subsequent protocol amendment at such time.

An alternative dosing schedule of BMS-986218 Q2W will also be explored to further characterize the safety, PK, and pharmacodynamics of BMS-986218. Up to approximately 72 DLT-evaluable participants will be treated with 10, 20, 35, 50, 75, and 100 mg Q2W during the BMS-986218 Monotherapy Escalation (Part 1A) of the study for the Q2W schedule. The Q2W dosing schedule will start at a total dose level equivalent to a dose that has cleared safety in the Q4W dosing cohort (eg, 10 mg Q2W vs 20 mg Q4W), and continue evaluating higher doses up to the MTD equivalent of the Q4W dosing cohort. If supported by clinical and safety data, doses higher than 100 mg Q2W may be studied, and will be guided by Q4W equivalent doses that have cleared safety until MTD equivalent of the Q4W dosing cohort is reached. Based on the preliminary PK from the Q4W dosing cohorts, at the steady state, the Q2W dosing schedule is projected to provide approximately the same AUCtau (tau = 4 weeks) as Q4W dosing schedule, and approximately 70% Cmax as Q4W dosing schedule.

Additionally, participants with advanced stage cutaneous melanoma, microsatellite stable colorectal cancer (MSS CRC), NSCLC, or SCCHN will be treated with BMS-986218 on a Q2W schedule at a starting dose of 20 mg in the Part 1A pharmacodynamic (PD) cohort. Based on preliminary analysis of Treg count decrease in the tumor microenvironment, using single-cell ribonucleic acid (RNA) sequencing gene expression analysis, additional cohorts of participants at higher dose levels may be evaluated. For example, if the expected PD activity is not observed after 5 to 10 evaluable participants at the 20 mg dose level, then the next set of 5 to 10 evaluable participants may be treated at a higher dose level or Q4W schedule. Therefore, more than one dose level may be evaluated based on the PD results assessment.

Any additional dose levels evaluated in the Q2W schedule of the Part 1A PD cohort will be a dose that has been determined to be safe and tolerable in either the Q2W escalation part or a dose equivalent to the Q4W dose, which has been determined to be safe and tolerable in the Q4W dose escalation part. Approximately 20 evaluable participants per dose level (per dose schedule) may be treated as part of the PD cohort. Each participant will be administered IV doses of BMS-986218 Q2W or Q4W per cycle, for up to 2 calendar years.

Prior to declaring the MTD, and in consultation with Investigators, the Sponsor has the option to expand any dose level previously established to be tolerable in order to obtain additional experience or to investigate dose levels intermediate to those defined in the protocol. Planned dose levels may be modified, or intermediate dose levels added, based upon the BLRM analysis and clinical evaluation of all available safety and PK/pharmacodynamic data. Once the tolerability (during the DLT evaluation) of a dose level has been established, additional participants may be added at that dose level to better characterize the safety, PK, and pharmacodynamic profiles (not to exceed a total of 200 evaluable participants across dose levels and schedules). Additional information on DLTs can be found in [Section 7.6.1](#).

### **Sentinel Participant:**

During the dose-escalation phase, a staggered dosing (sentinel participant) approach will be used. The first participant to be dosed at C1D1 of each dose level will be observed for 5 days, before additional participants (ie, Participant 2 onward in that cohort) receive study treatments in the same dose level.

Initially, 3 participants will be enrolled at the start of each cohort, in accordance with the sentinel participant approach cited above. However, to allow for any unforeseen discontinuations (such as disease progression) before the 8-week DLT period (56 days) is completed, extra participants may be enrolled in each dose escalation cohort.

#### **5.1.2.2 *The Safety Evaluation of Combination Doses of BMS-986218 with Nivolumab (Part 1B)***

The Safety Evaluation of Combination Doses of BMS-986218 with Nivolumab (Part 1B) will be initiated starting at 1 dose level below current safety cleared Q4W monotherapy cohort, defined from BLRM and an overall assessment of all available safety, PK/pharmacodynamic, and efficacy data of the BMS-986218 Monotherapy Escalation (Part 1A).

In the Safety Evaluation of Combination Doses of BMS-986218 with Nivolumab (Part 1B), the starting dose of BMS-986218 was 1 dose level lower than the Q4W 40 mg monotherapy dose level of BMS-986218, which had demonstrated an acceptable safety profile and was administered in combination with nivolumab at the flat dose of 480 mg Q4W. Dose escalation and determination of MTD for the Safety Evaluation of Combination Doses of BMS-986218 with Nivolumab (Part 1B) will be guided by BLRM-copula. Subsequent dose selection of the combination will be based on evaluating the recommendation from BLRM-copula and an overall assessment of all available safety and PK/pharmacodynamic data. Safety evaluation and tumor assessment will be performed Q8W (2 cycles). If toxicity is unacceptable at any combination dose level, additional combination dose level(s) may be evaluated using BMS-986218 and/or nivolumab (eg, dose of 240 mg Q4W). Selection of dose level for each study drug will be based on the nature and attribution of observed DLTs in previously evaluated dose levels. An intermediate dose level of BMS-986218 and/or an intermediate dose level of nivolumab Q4W may be evaluated in additional cohort(s). No intra-subject dose escalation or de-escalation of BMS-986218 or nivolumab is allowed at any dose level.

At no time will the dose of BMS-986218 in the Safety Evaluation of Combination Doses of BMS-986218 with Nivolumab (Part 1B) exceed the highest tolerated dose in the BMS-986218 Monotherapy Escalation (Part 1A). Dose escalation in each cohort, within the constraints cited above, will be enrolled in parallel. Up to approximately 84 DLT-evaluable participants will be enrolled in Part 1B. Additional information on DLTs can be found in [Section 7.6.1](#).

### **Sentinel Participant:**

The sentinel participant rule will be followed. The first participant to be dosed at Cycle 1 Day 1 of each dose level will be observed for 5 days, before additional participants (ie, Participant 2 onward in that cohort) receive study treatments at the same dose level. Initially, 3 participants will be enrolled at the start of each cohort, in accordance with the sentinel participant approach cited

above; however, to allow for any unforeseen discontinuations (eg, disease progression) before the 8-week DLT period (56 days) is completed, extra participants may be enrolled in each dose cohort.

### **5.1.2.3 *Dose Escalation Decisions for the BMS-986218 Monotherapy Escalation (Part 1A) and the Safety Evaluation of Combination Doses of BMS-986218 with Nivolumab (Part 1B)***

The dose-escalation phase of the study will evaluate the safety and tolerability of BMS-986218, given alone or in combination with nivolumab, based on DLTs, using a BLRM (for the BMS-986218 Monotherapy Escalation [Part 1A]) and a BLRM-copula (for the Safety Evaluation of Combination Doses of BMS-986218 with Nivolumab [Part 1B]).

During the monotherapy and combination therapy dose-escalation phase, a set of approximately 3 participants will be treated at each specified dose level. Cohort tolerability assessment with subsequent participant enrollment and dose recommendation will occur when at least 2 evaluable participants within a cohort have completed an 8-week DLT period. Any toxicities that occur beyond the DLT period will be accounted for in making dose level decisions and/or dose level modifications. Additional information on DLTs can be found in [Section 7.6.1](#).

If the potential DLT occurring in the third evaluable participant regarding the specific dose level does not influence the dose recommendation by BLRM or the BLRM-copula, the next dose level may proceed without waiting for the third participant to complete the corresponding DLT observation period, after discussion and agreement between the Sponsor and Investigators. Continuous re-assessment of dose recommendation, by BLRM in the BMS-986218 Monotherapy Escalation (Part 1A) and BLRM-copula in the Safety Evaluation of Combination Doses of BMS-986218 with Nivolumab (Part 1B), will be performed for each dose level. Planned dose levels for dose escalation are provided in [Table 5.5.2-1](#).

Planned dose levels may be modified, or intermediate dose levels added, based upon the BLRM-copula analysis for combination and clinical evaluation of all available safety and PK/pharmacodynamic data. Once the tolerability (during the DLT evaluation) of a dose level has been established, additional participants may be added at that dose level to better characterize the safety, PK, and pharmacodynamic profiles.

The monotherapy doses of BMS-986218, selected for the Randomized BMS-986218 Monotherapy Cohort Expansion in Cutaneous Melanoma (Part 2A), the BMS-986218 Cohort Expansion - Monotherapy (Part 2B), and the combination therapy doses of BMS 986218, selected for BMS-986218 Cohort Expansion - Combination Therapy in NSCLC (Part 2C) and BMS-986218 Cohort Expansion - Combination Therapy in MSS CRC (Part 2D) will be based on evaluating the recommendation from BLRM and an overall assessment of all available safety, PK/pharmacodynamic, and efficacy data.

#### **5.1.2.4 The Randomized BMS-986218 Monotherapy Cohort Expansion in Cutaneous Melanoma (Part 2A), the BMS-986218 Cohort Expansion - Monotherapy (Part 2B), and the BMS-986218 Cohort Expansion - Combination Therapy (Part 2C and Part 2D)**

The purpose of the BMS-986218 cohort expansions is to gather preliminary efficacy information in specific patient populations regarding BMS-986218 alone and in combination with nivolumab.

Continuous evaluation of toxicity events in the BMS-986218 cohort expansions will be performed throughout enrollment for all expansion cohorts. If, at any time, the aggregate rate of treatment-related toxicities meeting DLT criteria exceeds 33% across all participants treated in cohort expansions, the findings will be discussed, and further enrollment will be interrupted. Depending on the nature and grade of the toxicity, and after assessing the benefit-risk ratio, a new dose for all cohorts may be initiated at a previously tested lower dose level or at a dose level intermediate to previously tested lower dose levels.

The Randomized BMS-986218 Monotherapy Cohort Expansion in Cutaneous Melanoma (Part 2A) will evaluate the preliminary efficacy of BMS-986218 monotherapy relative to ipilimumab monotherapy in a cohort of participants with advanced cutaneous melanoma who have received prior immunotherapy with an anti-PD-1 or anti-PD-L1 containing regimen and must have progressive or recurrent disease after prior anti-PD-1/PD-L1 directed therapy. Participants must not have received prior anti-CTLA-4 therapy. Three dose levels or schedules for BMS-986218 from the Part 1A Q4W monotherapy escalation will be evaluated that have had at least 6 DLT evaluable participants and meet safety criteria: one at 7 mg Q4W, one at 20 mg Q4W, and one at 70 mg Q4W, and ipilimumab 3 mg/kg (Q3W, 3-week treatment cycle for up to a maximum of 4 doses [which are to be completed within 16 weeks of the first dose in case of any delays]).

In the BMS-986218 Monotherapy Cohort Expansion (Part 2B), the preliminary efficacy of BMS-986218 will be investigated in tumor types where ipilimumab did not demonstrate a sufficient level of efficacy in previous studies and tumors in which a high level of Treg infiltration correlates with a poor prognosis. The tumor types to be evaluated will include NSCLC (adenocarcinoma or squamous cell subtypes only; at least 22 participants required per study arm); other tumor types may be explored in the future. Participants will be randomized evenly across study arms. Three dose levels or schedules for BMS-986218 from the Part 1A Q4W monotherapy escalation will be evaluated that have had at least 6 DLT evaluable participants and meet safety criteria: one at 7 mg Q4W, one at 20 mg Q4W, and one at 70 mg Q4W. BMS-986218 will be administered for a maximum duration of 2 calendar years when dosed Q4W. Participants should have received and then progressed on or relapsed/recurrence after anti-PD-1/PD-L1 directed therapy in monotherapy or in combination with chemotherapy. Prior anti-CTLA-4 therapy is allowed for no more than 20% of participants.

In the BMS-986218 Combination Therapy Cohort Expansion in NSCLC (Part 2C) , the preliminary efficacy and safety of BMS-986218 in combination with nivolumab will be investigated in participants whose NSCLC has progressed or relapsed after anti-PD-1/PD-L1

therapy. Participants must not have received prior anti-CTLA-4 therapy in the advanced or metastatic setting. Any selected BMS-986218 Part 2C dose will not exceed the highest Part 1B administered dose that has cleared safety, with a minimum of 6 evaluable participants for Safety Evaluation. More than one dose may be evaluated in Part 2C. The dose(s) of BMS-986218 selected for Part 2C will be based on the totality of preliminary safety, PK, and PD data from Part 1 and Part 2. The nivolumab dose found to be tolerable in Part 1B will be used in Part 2C. In Part 2C, participants will be treated Q4W for up to 2 calendar years regardless of treatment delays.

In the BMS-986218 Combination Therapy Cohort Expansion in MSS CRC (Part 2D) the preliminary efficacy and safety of BMS-986218 in combination with nivolumab will be investigated in participants with MSS CRC who have progressed or relapsed on at least 1 prior standard therapy. Participants must not have received prior anti-CTLA-4 therapy in the advanced or metastatic setting. Any selected BMS-986218 Part 2D dose will not exceed the highest Part 1B administered dose that has cleared safety, with a minimum of 6 evaluable participants for Safety Evaluation. The dose of BMS-986218 selected for Part 2D will be based on the totality of preliminary safety, PK, and PD data from Part 1 and Part 2. The nivolumab dose found to be tolerable in Part 1B will be used in Part 2D. In Part 2D, participants will be treated Q4W for up to 2 calendar years regardless of treatment delays.

In all study parts, participants with unconfirmed progressive disease, stable disease (SD), partial response (PR), or complete response (CR) at the end of a given cycle will continue to the next treatment cycle. Participants will be allowed to continue study treatment until the first occurrence of any of the following:

- Completion of the maximum duration of study therapy (up to 2 calendar years for BMS-986218 Q4W ± nivolumab Q4W; up to 2 calendar years for BMS-986218 Q2W; up to a maximum of 4 doses for ipilimumab Q3W).
- Confirmed progressive disease defined by Response Evaluation Criteria in Solid Tumors (RECIST) v1.1 ([Appendix 5](#)) or per Prostate Cancer Working Group (PCWG 3) criteria for prostate ([Appendix 12](#)) unless participants meet criteria for treatment beyond progression ([Section 8.1.1](#)).
- Clinical deterioration suggesting that no further benefit from treatment is likely.
- Intolerability to therapy.
- Participant meets criteria for discontinuation of study treatment as shown in [Section 8.1](#).

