### **5.1.2.5 Treatment Beyond Progression**

Tumor progression and response endpoints will be assessed using RECIST v1.1 criteria for solid tumors ([Appendix 5](#)) or per PCWG 3 criteria for prostate ([Appendix 12](#)). Treatment beyond progression may be allowed in selected participants with initial RECIST v1.1/PCWG 3-defined progressive disease following discussion and agreement with the BMS Medical Monitor (or designee), if the benefit-risk assessment favors continued administration of study treatment (eg, participants are continuing to experience clinical benefit as assessed by the Investigator, tolerating treatment, and meeting other criteria, see [Section 8.1.1](#)).

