# **8 DISCONTINUATION CRITERIA**

## **8.1 Discontinuation from Study Treatment**

Participants MUST discontinue for any of the following reasons:

- Documented disease progression as defined by RECIST v1.1 ([Appendix 5](#)) or per PCWG 3 criteria for prostate ([Appendix 12](#)) unless participants meet criteria for treatment beyond progression ([Section 8.1.1](#)).
- Clinical deterioration while receiving active study therapy that, in the opinion of the Investigator, indicates that continued participation in the study is not in the best interest of the participant.
- Any drug-related AE occurring at any time that meets DLT criteria as outlined in [Section 7.6.1](#) will require permanent discontinuation. Exceptions to permanent discontinuation are listed in [Section 7.6.4](#).
- Participant's request to stop study treatment. Participants who request to discontinue study treatment will remain in the study and must continue to be followed for protocol-specified follow-up procedures. The only exception to this is when a participant specifically withdraws consent for any further contact with him/her or persons previously authorized by participant to provide this information.
- Any clinical AE, laboratory abnormality or intercurrent illness that, in the opinion of the Investigator, indicates that continued participation in the study is not in the best interest of the participant.
- Termination of the study by BMS.
- Loss of ability to freely provide consent through imprisonment or involuntarily incarceration for treatment of either a psychiatric or physical (eg, infectious disease) illness. (Note: Under specific circumstances, and only in countries where local regulations permit, a participant who has been imprisoned may be permitted to continue as a participant. Strict conditions apply and BMS approval is required.)
- Inability to comply with protocol.
- Discretion of the Investigator.
- Pregnancy.

- Individual participants with confirmed CR will be given the option to discontinue study therapy on a case-by-case basis after specific consultation and agreement between the Investigator and BMS Medical Monitor (or designee) in settings where benefit-risk justifies discontinuation of study therapy.
- Any event that leads to delay in dosing lasting > 8 weeks from the previous dose requires discontinuation, with the following exceptions:
  - Dosing delays for prolonged steroid tapers to manage drug-related AEs are allowed.

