### **8.1.1      *Treatment Beyond Progression***

As described in [Section 5.4.6](#), accumulating evidence indicates that a minority of patients with tumors treated with immunotherapy may derive clinical benefit despite initial evidence of progressive disease. Participants will be permitted to continue treatment beyond initial RECIST v1.1/PCWG 3-defined progressive disease (see [Appendix 5](#) and [Appendix 12](#)), as long as they meet the following criteria:

- Investigator-assessed clinical benefit, and no rapid disease progression.
- Continue to meet all other study protocol eligibility criteria.
- Tolerance of study treatment.
- Stable performance status.

- Treatment beyond progression will not delay an imminent intervention to prevent serious complications of disease progression (eg, CNS metastases).
- Participant provides written informed consent prior to receiving any additional nivolumab or BMS-986218 treatment, using an ICF describing any reasonably foreseeable risks or discomforts, or other alternative treatment options.

The assessment of clinical benefit should take into account whether the participant is clinically deteriorating and unlikely to receive further benefit from continued treatment. If the Investigator believes that the participant continues to achieve clinical benefit by continuing treatment with the study treatments, then the participant should remain on the trial and continue to receive monitoring according to the Schedule of Activities (see [Section 2](#)). All decisions to continue treatment beyond initial progression must be discussed with and agreed upon by the BMS Medical Monitor (or designee) prior to treatment beyond progression, and an assessment of the benefit-risk of continuing with study therapy must be documented in the study records (see [Appendix 2](#)).

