#### **8.1.1.1 Discontinuation Due to Further Progression (Confirmed Progression)**

Participants will continue to receive monitoring according to the on-treatment assessments in Section 2. Radiographic assessment, by CT (preferred) or MRI described in [Section 9.3.1](#), is required when participants continue post-progression treatment and should be performed at each scheduled tumor assessment, no later than 8 weeks  $\pm$  7 days following initial disease progression, to determine whether there has been continued progressive disease. If the Investigator believes that the participant continues to achieve clinical benefit by continuing treatment, the participant should remain on the trial and continue to receive monitoring according to the Schedule of Activities (Section 2). Participants should permanently discontinue study therapy upon evidence of further progression, defined as an additional 10% or greater increase in tumor burden volume from time of initial progression (including all target lesions and new measurable lesions). This includes an increase in the sum of diameters of all target lesions and/or the diameters of new measurable lesions compared to the time of initial progressive disease.

The tumor burden volume from time of initial progression should be used as the reference baseline for comparison with the post progression assessment.

Any new lesion considered non-measurable at the time of initial progression may become measurable and, therefore, must be included in the tumor burden measurement.

If the longest diameter increases to at least 10 mm (except for pathological lymph nodes, which must have a short axis of at least 15 mm), a lesion is considered measurable. In situations where the relative increase in total tumor burden by 10% is solely due to inclusion of new lesions that become measurable, these new lesions must demonstrate an absolute increase of at least 5 mm.

For statistical analyses that include the Investigator-assessed progression date, participants who continue treatment beyond initial Investigator-assessed, RECIST v1.1/PCWG 3-defined progression will be considered to have Investigator-assessed progressive disease at the time of the initial progression event.

For participants who discontinue post progression treatment with study therapy, additional radiographic assessments will be required until a new tumor-directed therapy is initiated.

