Scans will be submitted to an imaging core laboratory for review by BICR at a later date or at any time during the study at the Sponsor's discretion.

Tumor assessments at other timepoints may be performed if clinically indicated. Assessments of PR and CR must be confirmed at least 8 weeks after initial response. When participants are allowed to be treated beyond initial disease progression per RECIST v1.1 criteria, subsequent tumor assessment will continue Q8W until confirmation of tumor progression. Thereafter, participants will continue tumor assessment as described in the follow-up period. Changes in tumor measurements and tumor responses will be assessed by the Investigator per study design using RECIST v1.1 criteria or per PCWG 3 criteria for prostate. Investigators will also report the number and size of new lesions that appear while on study. The timepoint of tumor assessments will be reported on the eCRF based on the Investigator's assessment using RECIST v1.1 criteria or per PCWG 3 criteria for prostate. (See [Appendix 5](#) and [Appendix 12](#) for specifics of RECIST v1.1 criteria and PCWG 3 criteria to be utilized in this study, respectively.)

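### Section 5.1.2.4 lets dosing continue through an undefined unconfirmed progression, while Sections 5.1.2.5, 8.1 and 8.1.1 require a stop, or consent and Medical Monitor agreement, at initial progression

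*Combined protocol and SAP*

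**What the plan says.** Section 5.1.2.4 gives a continuation rule that covers every part of the study: "participants with unconfirmed progressive disease, stable disease (SD), partial response (PR), or complete response (CR) at the end of a given cycle will continue". The continuation is into the next treatment cycle. The section then lists events that end treatment, whichever comes first. One is confirmed progression under RECIST v1.1 or PCWG 3, with the Section 8.1.1 exception attached. The last is "Participant meets criteria for discontinuation of study treatment as shown in" Section 8.1.

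Other sections set the rule at an earlier point:

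- Section 8.1 makes discontinuation mandatory at "Documented disease progression as defined by RECIST v1.1" (or PCWG 3 for prostate) unless 8.1.1 is met. It does not ask for confirmation.
- Section 5.1.2.5, on agreement with the Medical Monitor: "Treatment beyond progression may be allowed in selected participants with initial RECIST v1.1/PCWG 3-defined progressive disease following discussion and agreement".
- Section 8.1.1 applies at initial progression and lists several criteria, among them "Participant provides written informed consent prior to receiving any additional nivolumab or BMS-986218 treatment". It adds: "All decisions to continue treatment beyond initial progression must be discussed with and agreed upon by the BMS Medical Monitor (or designee").
- Section 8.1.1.1, whose heading equates further progression with confirmed progression, requires permanent discontinuation at further progression, "defined as an additional 10% or greater increase in tumor burden volume from time of initial progression".
- Section 9.3.1, on participants treated beyond initial progression: "subsequent tumor assessment will continue Q8W until confirmation of tumor progression".

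**The concern.** The continuation sentence in 5.1.2.4 puts unconfirmed progression beside stable disease and response, as a status at which the next cycle simply follows. No consent or Medical Monitor step is attached. A coordinator who works from that sentence would dose a participant who, under 8.1, must stop or first satisfy 8.1.1.

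At stake are consent and drug exposure. BMS-986218 is a first-in-human antibody. Section 3.2.1.3 describes a more potent toxicity profile than ipilimumab in monkeys, and Section 3.3 says clinical benefit is not established. Consent at progression is the point at which the participant is told of the risks and of alternative treatments.

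A smaller, separate gap is that the 8.1.1 consent bullet names only nivolumab and BMS-986218. It therefore does not cover an ipilimumab dose given in Part 2A after a week-12 scan that shows progression.

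**Working it through.** **Tracing one participant.** The same two events give different actions depending on the section read.

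| Event | 5.1.2.4 sentence and confirmed-progression bullet | 5.1.2.5, 8.1, 8.1.1, 8.1.1.1 |
|---|---|---|
| First unequivocal RECIST progression | Continue, no condition | Stop, unless all 8.1.1 criteria are met first, including consent and Medical Monitor agreement |
| Further increase of 10% or more (confirmed progression in the 8.1.1.1 heading) | Stop, but the 8.1.1 exception is still available | Permanent stop |

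The last bullet of 5.1.2.4 brings the right-hand column's 8.1 rule into the same list, so the section disagrees with itself.

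**Can a definition reconcile them?** The term unconfirmed progressive disease appears only in 5.1.2.4 and is not defined. Appendix 5, which that section cites, defines progression at a single assessment (its Section 3.1) and requires confirmation only for PR and CR (4.1.1). The findings that wait for a later scan are:

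- equivocal new lesions (Appendix 5, 3.3);
- an FDG-PET finding not confirmed by CT (Appendix 5, 3.3.1);
- PCWG3 bone findings (Appendix 12, 2.2.2) and equivocal progression (Appendix 12, 2.3.4), in prostate cancer only.

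There is no general confirmation step for progression. Elsewhere, 8.1.1.1 and 9.3.1 use confirmed or confirmation for the later, further-progression step. Carried back to 5.1.2.4, that meaning produces the conflict directly.

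**Doses between first progression and the next scan.** Inputs: Q4W and Q2W dosing; scans every 8 weeks and before the next cycle; in Part 2A the first scan is at week 12, then every 8 weeks (Sections 5.1.2 and 9.3). Nominal times are used.

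- Q4W, progression at week 8, next scan at week 16: doses at weeks 8 and 12, that is (16 − 8)/4 = 2.
- Q2W, same scans: doses at weeks 8, 10, 12 and 14, that is (16 − 8)/2 = 4.
- Part 2A BMS-986218, progression at week 12, next scan at week 20: doses at weeks 12 and 16, that is (20 − 12)/4 = 2.
- In the combination parts, each of the 2 Q4W visits delivers both drugs.

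**Ipilimumab.** There are four doses at 3-week spacing, nominally at weeks 0, 3, 6 and 9, to be completed within 16 weeks of the first (5.1.2.4). The week-12 scan is held regardless of dose delays (Table 2-4).

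- On schedule: 0 doses after week 12.
- Slack for dose 4: 16 − 9 = 7 weeks. Dose 4 falls at or after week 12 if the cumulative delay is 3 to 7 weeks, giving 1 dose.
- Doses 3 and 4 both fall there only if dose 3 is 6 or 7 weeks late (weeks 12 and 15, or 13 and 16), giving 2 doses. A third would need 12 + 6 = 18 weeks, past the limit.
- Section 8.1 requires discontinuation, with exceptions, if dosing is delayed more than 8 weeks from the previous dose. With dose 2 on time at week 3 and dose 3 at week 12, the gap is 12 − 3 = 9 weeks, which breaches it. With dose 2 delayed to week 4 the gap is 12 − 4 = 8 weeks, which does not. The maximum of 2 is therefore reachable, but only if dose 2 is also late or an exception applies.

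**The case against.** The strongest reply is that the protocol already resolves this. The 5.1.2.4 list ends treatment at whichever event comes first, and its last bullet imports 8.1, so the stricter rule wins. Section 5.1.2.5 follows immediately and requires Medical Monitor agreement at initial progression. Section 5.1.2 ties further cycles to confirmed clinical benefit. That stands: read as a whole, the protocol does not authorise dosing after progression without consent, and this limits the practical effect. It does not remove an unconditional instruction to continue that only a cross-reference corrects.

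A second reply is that confirmed means established under the appendices, and unconfirmed means the findings those appendices leave open. This is sensible and probably what was meant. It also explains why the confirmed-progression bullet carries an 8.1.1 exception, which would be pointless if confirmed meant further progression. But no text says so, and findings left open in this way do not yet count as progression.

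On ipilimumab, it is fair that exposure is 0 doses on schedule, that the drug is given at its approved dose, and that the Medical Monitor steps cover it anyway. The ±1-week scan window also shifts the delay thresholds. The consent bullet still omits ipilimumab. Finally, the issue is better described as an internal inconsistency than a design choice, since the intended design is clear from the other sections.

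**Conclusion.** The concern holds. Section 5.1.2.4 conflicts with 5.1.2.5, 8.1 and 8.1.1 at initial progression, with 8.1.1.1 at further progression, and with its own last bullet. It should be corrected.

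For a site that follows the sentence alone, the exposure without the required steps is up to 2 Q4W or 4 Q2W doses before the next scan. For ipilimumab, 0 doses on schedule and at most 2 after delays fall outside the consent bullet. These counts assume nominal visit and scan times, with each scan done before the dose due at that visit. The documents give no basis for estimating how many participants would be affected.

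Efficacy results are not at risk from this point. Section 8.1.1.1 dates progression at the initial event even when treatment continues, and Appendix 5 (4.2) closes best overall response at documented progression.

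**What to change.** 1. In 5.1.2.4, replace the continuation sentence. Participants with SD, PR or CR continue. So do those with findings that do not yet meet the definition of progression: equivocal new lesions, FDG-PET findings awaiting CT, and PCWG3 bone or equivocal findings awaiting a later scan. Participants with initial RECIST v1.1 or PCWG 3 progression continue only if all Section 8.1.1 criteria, including signed consent and documented Medical Monitor agreement, are met before the next dose.
2. Replace the confirmed-progression bullet in 5.1.2.4 with two stops: initial progression unless 8.1.1 is met (as in 8.1), and permanent discontinuation at an additional increase of 10% or more (as in 8.1.1.1).
3. In the 8.1.1 consent bullet, refer to any additional study treatment instead of naming two drugs.

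The cost is amendment wording in Sections 5.1.2.4 and 8.1.1, with no extra visits, participants or system changes. The amendment needs the usual ethics approval (Appendix 2). The third change may also need matching consent-form text for ipilimumab; the consent forms were not available to check.
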